5.10 Randomization/Drug Assignment

Interactive Response Technology (IRT) will be utilized to register (screen and randomize) subjects on study. The site will contact the IRT to obtain a screening (subject) number only after the subject has signed the informed consent and prior to any study-specific procedures being performed (e.g., labs are drawn). Subjects who satisfy all eligibility criteria at Screening will proceed to being randomized based

on baseline platelet counts determined within 24 hours prior to the first dose. The site will contact the IRT to complete the randomization process and obtain study drug assignment.

The IRT will randomize subjects into 2 treatment arms using 1:1 randomization ratio. Randomization will be stratified by:

- Intermediate-2 versus high risk (DIPSS+)
- Platelet count $\leq 200 \times 10^9/L$ versus $> 200 \times 10^9/L$ (determined within 24 hours prior to first dose)

Blinding of Investigational Product

All AbbVie personnel with direct oversight of the conduct and management of the trial (with the exception of AbbVie Drug Supply Management Team), the investigator, study site personnel, and the subject will remain blinded to each subject's treatment throughout the study. To maintain the blind, the navitoclax film-coated tablets and placebo-film-coated tablets provided for the study will be identical in appearance.

The IRT will provide access to unblinded subject treatment information in the case of a medical emergency. AbbVie must then be notified within 24 hours of the blind being broken. The date and reason that the blind was broken must be recorded in the source documentation and electronic case report form (eCRF), as applicable.

5.11 Protocol Deviations

AbbVie does not allow intentional/prospective deviations from the protocol except when necessary to eliminate an immediate hazard to study subjects. The investigator is responsible for complying with all protocol requirements, written instructions, and applicable laws regarding protocol deviations. If a protocol deviation occurs (or is identified, including those that may be due to the COVID-19 pandemic), the investigator is responsible for notifying independent ethics committee (IEC)/independent review board (IRB), regulatory authorities (as applicable), and AbbVie.

5.12 Data Monitoring Committee

An IDMC will regularly review unblinded safety data from the ongoing study, once every 6 months, according to the schedule provided in the IDMC charter, including adverse events and laboratory results. The unblinded safety analyses will be performed by an independent statistical data analysis center (SDAC) external to AbbVie and reviewed by the IDMC. AbbVie personnel will remain blinded and will not have access to the unblinded analyses prepared for the IDMC. The IDMC will provide recommendations to AbbVie as per the IDMC charter including any modifications to the protocol or discontinuations of the study.

A separate IDMC charter will be prepared outside of the protocol that will further describe the IDMC membership (which will include individuals with experience in treatment of patients with myeloproliferative neoplasms), roles and responsibilities of the IDMC members, frequency and scope of the data reviews, and expectations for blinded communications.

6 SAFETY CONSIDERATIONS

6.1 Complaints and Adverse Events

Complaints

A complaint is any written, electronic, or oral communication that alleges deficiencies related to the physical characteristics, identity, quality, purity, potency, durability, reliability, safety, effectiveness, or performance of a product/device. Complaints associated with any component of this investigational product must be reported to AbbVie.

Product Complaint

A product complaint is any complaint related to the biologic or drug component of the product or to the medical device component(s).

For a product this may include, but is not limited to, damaged/broken product or packaging, product appearance whose color/markings do not match the labeling, labeling discrepancies/inadequacies in the labeling/instructions (e.g., printing illegible), missing components/product, device not working properly, or packaging issues.

Product complaints concerning the investigational product and/or device must be reported to AbbVie within 24 hours of the study site's knowledge of the event. Product complaints occurring during the study will be followed up to a satisfactory conclusion.

Medical Complaints/Adverse Events and Serious Adverse Events

An adverse event is defined as any untoward medical occurrence in a subject or clinical investigation subject administered a pharmaceutical product and which does not necessarily have a causal relationship with this treatment. An adverse event can therefore be any unfavorable and unintended sign (including an abnormal laboratory finding), symptom, or disease temporally associated with the use of a medicinal (investigational) product, whether or not the event is considered causally related to the use of the product.

Such an event can result from use of the drug as stipulated in the protocol or labeling, as well as from "special situations," such as accidental or intentional overdose, medication error, occupational or accidental exposure, off-label use, drug abuse, drug misuse, or drug withdrawal, all which must be reported whether associated with an adverse event or not. Any worsening of a pre-existing condition or illness is considered an adverse event. Worsening of disease under study or underlying cancer (serious or nonserious event) should be collected as an adverse event due to disease progression on the eCRF. Worsening in severity of a reported adverse event should be reported as a new adverse event. Laboratory abnormalities and changes in vital signs are considered to be adverse events only if they result in discontinuation from the study, necessitate therapeutic medical intervention, meets protocol specific criteria (see Section 6.2 regarding toxicity management), and/or if the investigator considers them to be adverse events.

The investigators will monitor each subject for clinical and laboratory evidence of adverse events on a routine basis throughout the study. All adverse events will be followed to a satisfactory conclusion.

An elective surgery/procedure scheduled to occur during a study will not be considered an adverse event if the surgery/procedure is being performed for a pre-existing condition and/or the surgery/procedure has been pre-planned prior to study entry. However, if the pre-existing condition deteriorates unexpectedly during the study (e.g., surgery performed earlier than planned), then the deterioration of the condition for which the elective surgery/procedure is being done will be considered an adverse event. Hospitalization for the purpose of monitoring platelet counts post study drug administration is not considered an adverse event or serious adverse event. If the hospitalization is prolonged due to an event not related to monitoring platelet counts, then adverse event/serious adverse event criteria is to be assessed.

If an adverse event, whether associated with study drug or not, meets any of the following criteria, it is to be reported to AbbVie clinical pharmacovigilance as a serious adverse event within 24 hours of the site being made aware of the serious adverse event (refer to Section 4.2 of the Operations Manual for reporting details and contact information):

Death of Subject	An event that results in the death of a subject.
Life-Threatening	An event that, in the opinion of the investigator, would have resulted in immediate fatality if medical intervention had not been taken. This does not include an event that would have been fatal if it had occurred in a more severe form.
Hospitalization or Prolongation of Hospitalization	An event that results in an admission to the hospital for any length of time or prolongs the subject's hospital stay. This does not include an emergency room visit or admission to an outpatient facility.
Congenital Anomaly	An anomaly detected at or after birth, or any anomaly that results in fetal loss.
Persistent or Significant Disability/Incapacity	An event that results in a condition that substantially interferes with the activities of daily living of a study subject. Disability is not intended to include experiences of relatively minor medical significance such as headache, nausea, vomiting, diarrhea, influenza, and accidental trauma (e.g., sprained ankle).

Important Medical Event Requiring Medical or Surgical Intervention to Prevent Serious Outcome

An important medical event that may not be immediately life-threatening or result in death or hospitalization, but based on medical judgment may jeopardize the subject and may require medical or surgical intervention to prevent any of the outcomes listed above (i.e., death of subject, life threatening, hospitalization, prolongation of hospitalization, congenital anomaly, or persistent or significant disability/incapacity). Additionally, any elective or spontaneous abortion or stillbirth is considered an important medical event. Examples of such events include allergic bronchospasm requiring intensive treatment in an emergency room or at home, blood dyscrasias or convulsions that do not result in inpatient hospitalization, or the development of drug dependency or drug abuse.

All adverse events reported from the time of study drug administration until 30 days after the last dose/discontinuation of study drug administration will be collected, whether solicited or spontaneously reported by the subject. In addition, study procedure-related serious and nonserious adverse events will be collected from the time the subject signs the study-specific informed consent.

The following definitions will be used for serious adverse reactions (SARs) and suspected unexpected serious adverse reactions (SUSARs):

SAR Defined as all noxious and unintended responses to an Investigational Medicinal Product (IMP) related to any dose administered that result in death, are life-threatening, require inpatient hospitalization or prolongation of existing hospitalization, result in persistent or significant disability or incapacity, or are a congenital anomaly or birth defect.

SUSAR A suspected SAR: refers to individual serious adverse event (SAE) case reports from clinical trials where a causal relationship between the SAE and the IMP was suspected by either the Sponsor or the investigator, is not listed in the applicable Reference Safety Information (RSI), and meets one of the following serious criteria: results in death, is life-threatening, requires hospitalization or prolongation of an existing hospitalization, results in persistent or significant disability or incapacity, or is a congenital anomaly or birth defect. All individually reported SARs are considered suspected.

AbbVie will be responsible for SUSAR reporting for the investigational medicinal product (IMP) in accordance with global and local regulatory requirements in participating countries.

Adverse events will be monitored throughout the study to identify any of special interest that may indicate a trend or risk to subjects.

Adverse Event Severity and Relationship to Study Drug

The investigator will rate the severity of each adverse event according to the National Cancer Institute (NCI) Common Terminology Criteria for Adverse Events (CTCAE) version 5.0. If a reported adverse event increases in severity, the initial adverse event should be given an end date and a new adverse event must be reported with a different onset date than the end date of the previous adverse event to reflect the change in severity. The dates of the adverse events cannot overlap.

For adverse events not captured by the NCI CTCAE, the following criteria should be used:

Grade 1	Mild; asymptomatic or mild symptoms; clinical diagnostic observations only; intervention not indicated.
Grade 2	Moderate; minimal, local or noninvasive intervention indicated; limiting age-appropriate instrumental activities of daily living.
Grade 3	Severe or medically significant but not immediately life-threatening; hospitalization or prolongation of hospitalization indicated; disabling; limiting self-care activities of daily living.
Grade 4	Life-threatening consequences; urgent intervention indicated.
Grade 5	Death related to AE.

For all reported serious adverse events that increase in severity, the supplemental eCRFs also need to be updated to reflect any changes due to the increase in severity. For serious adverse events considered as having "no reasonable possibility" of being associated with study drug, the investigator will provide an "other" cause of the event.

The investigator will use the following definitions to assess the relationship of an adverse event to the use of study drug:

Reasonable Possibility	After consideration of factors including timing of the event, biologic plausibility, clinical judgment, and potential alternative causes, there is sufficient evidence (information) to suggest a causal relationship.
No Reasonable Possibility	After consideration of factors including timing of the event, biologic plausibility, clinical judgment, and potential alternative causes, there is insufficient evidence (information) to suggest a causal relationship.

The investigator will assess the relationship of each adverse event to navitoclax and, if applicable, to ruxolitinib. For causality assessments, events assessed as having a reasonable possibility of being related to the study drug will be considered "associated." Events assessed as having no reasonable possibility of being related to study drug will be considered "not associated." In addition, when the investigator has not reported causality or deemed it not assessable, AbbVie will consider the event associated.

Pregnancy

While not an adverse event, pregnancy in a study subject must be reported to AbbVie within 24 hours after the site becomes aware of the pregnancy. Subjects who become pregnant during the study must be discontinued (Section 5.5). If a pregnancy occurs in a study subject or in the partner of a study subject, information regarding the pregnancy and the outcome will be collected.

In the event of pregnancy occurring in a subject's partner during the study, written informed consent from the partner must be obtained prior to collection of any such information. AbbVie will provide a separate consent form for this purpose. Pregnancy in a subject's partners will be collected from the date of the first dose through 30 days following the last dose of study drug.

The pregnancy outcome of an elective or spontaneous abortion, stillbirth or congenital anomaly is considered a SAE and must be reported to AbbVie within 24 hours after the site becomes aware of the event.

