4.2 Discussion of Study Design

Choice of Control Group

Ruxolitinib is the current standard treatment that is approved for patients with MF and induces improvement in splenomegaly and disease-related symptoms compared with placebo or best available therapy.² This study compares navitoclax in combination with ruxolitinib to placebo in combination with ruxolitinib. The choice of control group allows for a double-blind assessment of the contribution of navitoclax to the safety and efficacy of the backbone treatment of ruxolitinib.

Appropriateness of Measurements

Standard statistical, clinical, and laboratory procedures will be utilized in this study. All efficacy measurements in this study are standard for assessing disease activity in subjects with MF. All clinical and laboratory procedures in this study are standard and generally accepted.

Suitability of Subject Population

JAK2 inhibition induces down-regulation of the anti-apoptotic protein myeloid cell leukemia 1 (MCL-1) suggesting a role for navitoclax, a BCL-XL inhibitor, in the treatment of myeloproliferative neoplasms including MF. Therefore, subjects diagnosed with MF (PMF or SMF) represent the target population for this study.

Selection of Doses in the Study

The recommended starting dose of ruxolitinib for MF is according to the approved label and is based on the subject's baseline platelet count determined within 24 hours prior to the first dose: 20 mg twice daily ($> 200 \times 10^9/L$) or 15 mg twice daily ($100 \times 10^9/L$ to $200 \times 10^9/L$). The investigator may adjust the starting dose of ruxolitinib as medically appropriate after consultation with the AbbVie TA MD/SD, with subsequent increase in dose as shown in [Table 1](#).

As a BCL-X_L inhibitor, navitoclax causes thrombocytopenia via intravascular apoptosis of platelets. AbbVie internal data indicate that the effect of navitoclax on platelet reduction is exposure-related but may be diminished upon continued administration. Accordingly, thrombocytopenia may occur with navitoclax upon exposure to sufficient navitoclax concentrations. Additionally, thrombocytopenia and anemia are the primary reasons for ruxolitinib dose reductions.¹²

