5.5 Subject Discontinuation from Study Drug Treatment and Discontinuation of Study

Treatment with study drug may continue until end of clinical benefit or occurrence of unacceptable toxicity or discontinuation from study. A subject may voluntarily withdraw or be withdrawn from study drug treatment at any time for reasons including, but not limited to, the following:

- The subject is no longer deriving clinical benefit from study drug treatment, has disease progression, or the investigator believes it is in the best interests of the subject.
- The subject requires alternative therapy for treatment of MF.
- Clinically significant abnormal laboratory results or AEs, which rule out continuation of the study drug, as determined by the investigator or the AbbVie TA MD.
- Eligibility criteria violation was noted after the subject started study drug and continuation of the study drug would place the subject at risk.

- Introduction of prohibited medications and continuation of the study drug would place the subject at risk.
- The subject becomes pregnant while on study drug, or begins or intends breastfeeding.
- Significant subject noncompliance with study drug administration, study procedures, or study requirements, which would put the subject at risk for continued participation in the trial.
- The subject withdraws consent to receiving study drug treatment.
- Any other medical reason that AbbVie or the investigator deems appropriate.
- If the study treatment is unblinded by the investigator, that subject would need to be discontinued from study treatment and post-treatment or survival follow-up would commence.

Withdrawal from study (including all follow-up) will occur under the following circumstances:

- Withdrawal of consent for follow-up (this request must be documented in the subject's medical records and signed by the investigator)
- Lost to follow-up
- Death of subject
- Study termination by Sponsor.

Discussion with the TA MD/SD is recommended prior to discontinuation of a subject from study treatment for any reason other than described above to ensure all acceptable mitigation steps have been evaluated.

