5.6 Follow-Up After Subject Discontinuation of Study Drug or from Study

To minimize missing data for efficacy and safety assessments, subjects should be advised on the continued scientific importance of their data even if they discontinue treatment with study drug early. Subjects who discontinue study drug treatment should continue on study with all assessments conducted through post-treatment follow-up visits and survival follow up (per the Operations Manual, Section 2.2) until death, subject withdrawal from study participation (i.e., withdrawal of informed consent) or study termination, whichever occurs first.

If a subject withdraws from study follow up or withdraws permission for the collection of their personal data, the study staff may still use available public records to obtain information about survival status only, as appropriate per local regulations.

In the event a subject withdraws consent from the clinical study, biomarker research will continue unless the subject explicitly requests analysis to be stopped. When AbbVie is informed the subject has withdrawn and no longer wishes biomarker samples research to continue, samples will not be analyzed, and no new biomarker analysis data will be collected for the withdrawn subject or added to the existing data or database(s). A subject may withdraw consent for optional biomarker research at any time and remain in the clinical study. Data generated from clinical study and/or optional biomarker research before subject withdrawal of consent, will remain part of the study results.

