9.2.2 Adverse Event Overview

An overview of AEs will be presented consisting of the number and percentage of subjects experiencing at least one event for each of the following AE categories:

- Any treatment-emergent AE
- Any treatment-emergent AE with NCI toxicity Grade ≥ 3
- Any treatment-emergent AE with NCI toxicity Grade 3 or 4
- Any treatment-emergent AE with NCI toxicity Grade 3
- Any treatment-emergent AE with NCI toxicity Grade 4
- Any treatment-emergent AE with reasonable possibility related to navitoclax/placebo as assessed by the investigator
- Any treatment-emergent AE with reasonable possibility related to ruxolitinib as assessed by the investigator
- Any serious treatment-emergent AE
- Any treatment-emergent AE leading to discontinuation of navitoclax/placebo
- Any treatment-emergent AE leading to discontinuation of ruxolitinib

- Any treatment-emergent AE leading to interruption of navitoclax/placebo
- Any treatment-emergent AE leading to interruption of ruxolitinib
- Any treatment-emergent AE leading to dose reduction of navitoclax/placebo
- Any treatment-emergent AE leading to dose reduction of ruxolitinib
- Any treatment-emergent AE leading to death
- Any treatment-emergent AE related to COVID-19 infection
- All deaths
- Deaths occurring within 30 days after the last dose of study drug
- Deaths occurring more than 30 days after the last dose of study drug
- Deaths related to COVID-19 infection

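### Protocol 6.1 ties one adverse-event trigger to leaving the study rather than to stopping or changing study drug, which leaves a narrow gap in the SAP 9.2.2 tolerability rows

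*Protocol*

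**What the plan says.** Protocol 6.1 sets a restrictive rule for laboratory and vital-sign changes: "Laboratory abnormalities and changes in vital signs are considered to be adverse events only if they result in discontinuation from the study". The same sentence gives three more routes, joined by and/or. The finding may "necessitate therapeutic medical intervention", or it may satisfy the last two: "meets protocol specific criteria (see Section 6.2 regarding toxicity management), and/or if the investigator considers them to be adverse events".

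Protocol 5.5 keeps leaving treatment apart from leaving the study. Among the reasons for stopping study drug is "Clinically significant abnormal laboratory results or AEs, which rule out continuation of the study drug". A separate list opens with "Withdrawal from study (including all follow-up) will occur under the following circumstances" and has four entries: withdrawn consent for follow-up, loss to follow-up, death, and termination by the sponsor. Protocol 5.6 then adds: "Subjects who discontinue study drug treatment should continue on study with all assessments".

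SAP 9.2.2 reports tolerability in six rows: treatment-emergent adverse events leading to discontinuation, interruption or dose reduction, each for navitoclax/placebo and for ruxolitinib. One of them is "Any treatment-emergent AE leading to dose reduction of ruxolitinib".

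**The concern.** The first trigger appears meant to catch laboratory findings serious enough to end treatment, but it is worded in terms of leaving the study. Under 5.5 and 5.6 a subject whose drug is stopped for a laboratory value normally stays on study, so the trigger misses that case. Section 5.5 also names laboratory results beside adverse events as a distinct reason for stopping drug, so a laboratory-driven stop without an adverse event is something the protocol itself allows for.

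At stake is the completeness of the six SAP rows. A stop, interruption or reduction that is never recorded as an adverse event is absent from them. Where recording rests on investigator judgement, the rows may also vary between sites, of which about 190 are planned.

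**Working it through.** The plan states no figure on this point, so the check is a comparison of texts.

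**Step 1. Does the first trigger fit the protocol's terms?** None of the four study-withdrawal entries in 5.5 is a laboratory result. Laboratory results appear only in the drug-stopping list, and 5.6 keeps those subjects on study. The trigger is inconsistent with these sections.

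**Step 2. Is a study-drug action a trigger anywhere in the sentence?** No. The four routes are leaving the study, treatment, Section 6.2 criteria, and judgement.

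**Step 3. Which laboratory-driven actions are still captured?**

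| Reason for the action | Route that captures it |
|---|---|
| Platelet count or ANC under Table 1 | Section 6.2 criteria |
| Grade 3 or higher AST, ALT or bilirubin attributed to study drug | Section 6.2 criteria |
| Any abnormality treated, for example with transfusion or G-CSF | Treatment |
| Hemoglobin without transfusion, creatinine, blood pressure or pulse; untreated | Investigator judgement only |

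Only the last line can be lost, and only when the investigator does not call the finding an adverse event.

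**Step 4. Could the last line occur?** Protocol 4.2 says, citing a publication, that "thrombocytopenia and anemia are the primary reasons for ruxolitinib dose reductions". Table 1 has no hemoglobin row. Section 5.3 does not permit erythropoietin or danazol during treatment, so for anemia the treatment route rests largely on transfusion. Section 6.2 opens by mentioning dose delay or reduction for renal toxicities but gives no threshold.

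**Step 5. How clear is the Section 6.2 route?** Section 6.2 is written as dosing guidance and does not say which of its criteria define an adverse event. Table 1 includes rows under which a dose is maintained or increased, so not every row can count. It also has a ruxolitinib reduction in the platelet band from 100 to below 125 × 10⁹/L, while the eligibility criteria admit subjects from 100 × 10⁹/L. Sites could differ on whether a count in that band is an adverse event.

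**Step 6. Do other outputs show the lost actions?**
- SAP 5.0 tabulates all reasons and the primary reason for stopping study drug, with no adverse-event record needed. This partly covers the two discontinuation rows. SAP 4.0 defines study drug as any component of the combination, and SAP 5.0 does not say that the two drugs are shown separately.
- SAP 6.0 gives relative dose intensity by drug and arm. It reflects interruptions and reductions but not their reasons.
- SAP 9.3 gives graded laboratory shifts and listings of Grade 3 to 4 values. It does not link a value to a dose action.

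No planned table gives reasons for interruptions or reductions without an adverse event, so four of the six rows have no counterpart.

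**Step 7. Scale.** If the 230 planned subjects split evenly and all are treated, each arm has 230 / 2 = 115, and one missed subject is 1 / 115 = 0.87 percentage points of a row. The documents give nothing from which to estimate how many subjects would be missed.

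**The case against.** The strongest reply is that the sentence has four routes, and reading the first alone misleads. Platelets, neutrophils and liver tests come in through Section 6.2. The one dose-reduction figure from the earlier combination study (83% of subjects with a navitoclax reduction, thrombocytopenia being the primary reason, Protocol 4.2) concerns a cause that Table 1 covers. This stands, and it confines the point to a residue.

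Four further replies have weight:
- Section 6.1 also counts worsening of any pre-existing condition as an adverse event, which could take in worsening of baseline anemia. It may, but it sits unreconciled beside the *only if* wording.
- For ruxolitinib, Section 6.2 refers sites to the local label for all hematological and non-hematological toxicities, so hemoglobin or renal criteria might enter that way. The label is not in the documents, and 6.1 does not say that label criteria count.
- The protocol uses its terms loosely. The opening of 5.5 lists discontinuation from study among the ends of treatment, and its COVID-19 text foresees taking a subject off study for unlisted reasons. A site might read the trigger as covering the end of treatment.
- The Operations Manual is not available here and may already require a check of dose changes against adverse events.

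A reader might infer three stronger things that the documents do not support. The first is that the trigger can never be met: a laboratory abnormality could end in death, and the loose usage makes the wording ambiguous rather than empty. The second is that laboratory-driven dose changes in general drop out of the tables, which Step 3 contradicts. The third is that the navitoclax arm loses more events. That would need more actions outside Section 6.2 in that arm with similar recording in both, and no document shows either.

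**Conclusion.** The wording conflict between 6.1 and Sections 5.5 and 5.6 is real, and a study-drug action is not itself a trigger. The consequence is narrow. It concerns discontinuations, interruptions or reductions for values without an explicit Section 6.2 criterion that are untreated and not judged adverse events. Those can be missing from the SAP 9.2.2 rows, with partial cover from disposition for discontinuations and none with reasons for interruptions or reductions.

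The conclusion assumes that Section 6.2 criteria are read plainly as adverse-event criteria for platelets, neutrophils and liver tests. If sites read them more narrowly, the gap is wider. Any count of missed subjects would be a guess, and none is offered beyond the per-subject scale. No efficacy endpoint is affected. Severity: minor.

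**What to change.** 1. In Protocol 6.1, replace the phrase about leaving the study with discontinuation, interruption or dose reduction of navitoclax/placebo or ruxolitinib.
2. State in 6.1 which Section 6.2 criteria make a laboratory finding an adverse event, and whether local-label criteria for ruxolitinib count.
3. For subjects already treated, have data management query any dose change recorded with a laboratory or vital-sign reason and no linked adverse event.

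These steps change how events are recorded and leave every dose and clinical rule as it is. The cost is one phrase and one clarifying statement in the protocol, plus a data query. The downside is somewhat more adverse-event records and higher reported rates of adverse events leading to dose change.
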